## J. Subgroups of Analysis Populations

Not applicable.

Mundipharma-EDO GmbH / Protocol: EDO-S101-1004  
IQVIA Biotech (Confidential) Project # **CCI**

## K. Data Display Characteristics

Data displays produced for this study will include three types—summary tables, data listings, and figures. Unless stated otherwise, data listings will be produced for all recorded data. Additional data listings may be produced for outcome measures that involve extensive procedures to derive the analyzed outcomes. Summary tables will be produced as specified in following sections. Figures will be produced when specified in sections to follow.

Data listings will simply list the data recorded on the CRF or derived for each subject. They will be ordered by treatment, site, subject number, and time of assessment. When expedient, additional levels of ordering hierarchy may reflect subsets of assessments within subject. Data listings will not display subject initials.

Summary tables will display summary statistics calculated for each of the dose groups and all subjects combined, unless described otherwise in the following sections. For most summary tables, the dose group will be presented in a column and the summary statistics of interest will be presented in rows.

Continuous variables will be summarized using descriptive statistics (n, mean, standard deviation, median, minimum and maximum). Categorical variables will be summarized showing the number and percentage of patients within each classification.

## VI. Subject Accountability

### A. Subject Characteristics

The subject characteristics defined below will be presented in summary tables and data listings using data collected at the screening visit for subjects in the Safety Population. No formal statistical comparisons will be performed.

#### Demographics.

- *Age.* Age will be calculated as the number of years elapsed between birth date and the date of the screening visit, adjusted for whether the birthday has passed as of the day of the screening visit. (This corresponds to the typical calculation of age a person would use in conversation.)
- *Sex.* If Female, reproductive status will be summarized as well.
- *Race.* White or Caucasian, Black or African American, Asian, Other, Not Reported.
- *Ethnicity.* Hispanic, Not Hispanic, Unknown, Not Reported.

#### Baseline Characteristics.

Mundipharma-EDO GmbH / Protocol: EDO-S101-1004  
IQVIA Biotech (Confidential) Project # **CCI**

- *Height.*
- *Weight.*
- *Body Mass Index (BMI).* BMI will be calculated as the individual's body mass divided by the square of their height – with the value universally being given in units of kg/m^2.
- *Baseline ECOG Performance Status.*
- *Hematopoietic Cell Transplantation-Comorbidity Index (HCT-CI) Total Score at Screening.* The HCT-CI provides information with regard to the overall as well as non-relapse mortality risk a patient is likely to experience after SCT.
- *Baseline Left Ventricular Ejection Fraction (LVEF).*

Multiple Myeloma-Specific Diagnostic and Historical Information.

- *Disease Stage at Initial Diagnosis.*
- *Disease Stage at Current Diagnosis.*
- *Time Since Initial Diagnosis.* The number of months from date of original diagnosis to the date of informed consent.
- *Prior ASCT and all Other Previous Anti-Cancer Treatment.* Yes, No.
- *Best Response to Previous Anti-Cancer Treatment.*

Prior Cancer Treatment History.

- *Prior Cancer Treatment History.* The medically relevant prior cancer treatments reported by the patient will be coded using World Health Organization Drug Dictionary (WHO-DD) and raw and coded data will be summarized.

In addition, data listings will be provided for all the above baseline data.

## B. Disposition

A summary table of patient disposition as recorded during the End of Study visit will summarize the numbers for enrolled patients. Counts and percentages of patients who completed or withdrew for each of the reasons on the End of Study form will be calculated using the number of enrolled patients in the relevant cohort as the denominator. The reasons for end of study include:

- *Completed*
- *Adverse Event*
- *Death*
- *Engraftment Failure*

Mundipharma-EDO GmbH / Protocol: EDO-S101-1004  
IQVIA Biotech (Confidential) Project # **CCI**

- *Lost to Follow-Up*
- *Physician Decision*
- *Pregnancy*
- *Progressive Disease*
- *Screen Failure*
- *Study Terminated by Sponsor*
- *Subject Non-Compliance / Protocol Violations*
- *Withdrawal of Consent*

A listing of study exit data will also be generated for all enrolled patients in the Safety Population.

#### **C. Population Inclusions and Protocol Deviations**

A summary of the numbers and percentages of patients in each of the analysis sets (Safety Population, Full Analysis Set, Per-Protocol Population, Pharmacokinetic Population) for each dose cohort and overall will be prepared.

Protocol deviations are recorded in the Clinical Trial Management System, InfoLink2, and will be included in a data listing of deviations.

### **VII. Efficacy Analyses**

The Investigator's assessment of disease response will be used for patient management during the study. An Independent Review Committee (IRC) will provide an objective, unbiased, independent review of objective response, using the IMWG criteria (see [Table 6](#) in the protocol), as demonstrated based on the pertinent clinical data from the study. Response assessments as determined by the Investigator and IRC will be displayed.

Disease response assessment variables will be listed as reported on the eCRFs.

### **VIII. Safety Analyses**

Safety data, including changes from baseline, if applicable, will be summarized at each dose level for the Safety Population.

Additional safety analyses may be determined at any time without prejudice, in order to enumerate rates of toxicities most clearly, and to define further the safety profile of tinostamustine.

Mundipharma-EDO GmbH / Protocol: EDO-S101-1004  
IQVIA Biotech (Confidential) Project # **CCI**

#### A. Adverse Events

Per the protocol, Adverse Events will be collected from the time written informed consent is obtained through Day 100 ( $\pm 7$  days), or after the end of the study, if thought to be related to study drug, and will be defined as Treatment-Emergent Adverse Events (TEAE). Any events occurring prior to the tinostamustine dose are part of the subject's baseline status and will be recorded on the Medical History form.

If the start date of an adverse event is missing, the site will be queried to obtain the missing date. If that attempt is unsuccessful, the following rules will be applied to impute the start date of an adverse event:

- If the day (or the day and the month) are missing, but all other date components match with the first dose date of study drug, use the first dose date of study drug.
- If the day (or the day and the month) are missing, but some of the other date components do not match with the first dose date of study drug, use the earliest possible date. For example, use Jan 1 if the day and the month are missing; use the first day of the actual month if only the day is missing.
- If the day, month, and year are missing, use the first dose date of study drug, as long as the adverse event end date is not prior to the first dose date of study drug. Otherwise, do not impute.

AEs will be coded using MedDRA, associating lower-level terms with preferred terms and system organ classes by the primary hierarchy. The tables will display counts and percentages of patients who reported at least one AE in each system organ class represented in the AE data. Within each system organ class, the tables will display the counts and percentages of patients reporting at least one AE, as designated by the preferred terms. AE summaries will include treatment-emergent AEs (TEAEs).

Summary tables of TEAEs by default MedDRA System Organ Class (SOC) and Preferred Term (PT) will be sorted by decreasing order of frequency of SOC, and then, within that, by decreasing order of frequency of PT in the All Subjects group.

The following AE summary tables displaying counts and percentages of patients with adverse events will be produced:

- All TEAEs by Preferred Term.
- TEAEs by SOC, PT and Severity. On this table, treatment groups will be subdivided into five potential grades of AE severity, based on the National Cancer Institute (NCI) Common Terminology Criteria for Adverse Events (CTCAE version v4.03). An AE reported by a patient more than once will be represented in the most severe category.

Mundipharma-EDO GmbH / Protocol: EDO-S101-1004  
IQVIA Biotech (Confidential) Project # **CCI**

The AE listings shown here will be produced, sorted chronologically within patient. Each listing will include system organ class, preferred term, onset and end time, CTCAE grade, relation to each study drug, action taken with each study drug, outcome, type (DLT) and SAE status:

- All AEs.

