### 9.2.8.3. Recording Adverse Events

All AEs occurring from the time written informed consent is obtained through the Day 100 ( $\pm 7$  days) visit are to be recorded in the source documents and in the eCRF. AEs will be documented as occurring pre-conditioning (i.e., pre-tinostamustine); during conditioning (i.e., after the start of the first tinostamustine infusion through immediately before the start of ASC infusion); or after ASCT (i.e., after the start of ASC infusion). All AE reports are to contain the following details regarding the AE: a brief description, onset date, duration, intensity, treatment required, relationship to study drug, study drug action taken, outcome, and whether the event is classified as serious.

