## **D. Concomitant Medications**

Concomitant medication is defined as any medication with a start date within 28 days prior to the first dose of tinostamustine through Day 100 ( $\pm$  7 days). These medications will be documented as administered pre-conditioning (i.e., pre-tinostamustine); during conditioning (i.e., after the start of the first tinostamustine infusion through immediately before the start of autologous stem cell infusion); or after ASCT (i.e., after the start of ASC infusion). Any medication with a stop date prior to the first dose of study treatment is defined as a prior medication.

If the start date or the end date of a concomitant medication is missing, the following imputation rules will be applied:

Mundipharma-EDO GmbH / Protocol: EDO-S101-1004  
IQVIA Biotech (Confidential) Project # **CCI**

- For either the start or end date, if the year is missing or if the day, month, and year are all missing, do not impute.
- If both the start and stop dates are missing the month or day, the start date will be imputed first. If the imputed stop date is before the start date (imputed or non-imputed), then the stop date will be imputed using the start date.
- For the start date, if the day (or the day and the month) are missing, but all other date components match with the first dose date of study drug, use the first dose date of study drug. Otherwise, if the day (or the day and the month) are missing, but some of the other date components do not match with the first dose date of study drug, use the earliest possible date. For example, use Jan 1 if the day and the month are missing; use the first day of the actual month if only the day is missing.
- For the end date, if only the day is missing, use the last day of the month; if the day and the month are missing, use Dec 31.

Concomitant medications will be coded using the World Health Organization Drug Dictionary (WHO-DD). A separate summary table for each will be organized to display the anatomical main class (1st level) of each coded medication and, within that, the pharmacological subgroup (3rd level) of the coded medication. The summary tables will display counts and percentages of patients who reported using at least one medication in each represented pharmacological subgroup.

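### SAP VIII.A can place an adverse event's onset after its own end, because the partial-date rule lacks the end-date check used for wholly missing dates

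*SAP*

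**What the plan says.** SAP VIII.A first sends the problem back to the site: "the site will be queried to obtain the missing date". If that fails, three rules apply to the AE start date.

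- **First rule**, for a missing day (or day and month) where the known parts agree with the dosing date: "but all other date components match with the first dose date of study drug, use the first dose date of study drug". The end date plays no part.
- **Second rule**, for the same gaps where the known parts disagree: "but some of the other date components do not match with the first dose date of study drug, use the earliest possible date".
- **Third rule**, for a start date missing altogether: the dosing date is used, but only "as long as the adverse event end date is not prior to the first dose date of study drug". Otherwise nothing is imputed.

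Two other sentences in VIII.A decide which records reach these rules. AEs collected from consent through Day 100 are kept "and will be defined as Treatment-Emergent Adverse Events (TEAE"). Events before the dose belong to the subject's "baseline status and will be recorded on the Medical History form". The protocol differs on the second point. Section 9.2.8.3 has AEs recorded in the eCRF from consent onward, and "AEs will be documented as occurring pre-conditioning (i.e., pre-tinostamustine"), during conditioning, or after transplant.

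For medications, SAP VIII.D imputes a partial start date in the same way. Its only order check is "If the imputed stop date is before the start date (imputed or non-imputed), then the stop date will be imputed using the start date".

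**The concern.** The third rule shows that its authors foresaw a record whose event was over before dosing, and they protected that branch. The first rule assigns the same date to records that carry more information about onset, yet it disregards an end date that may be known. No other SAP rule caps an imputed AE start at the AE's end.

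At stake are the consistency of the AE dates and possibly the treatment-emergent AE (TEAE) tables. SAP I.C drops the DLT, engraftment-failure, treatment-related mortality and Grade 3 toxicity analyses after the study was stopped on safety signals. The TEAE tables by preferred term, and by system organ class, term and severity, are among the main safety summaries left. They are shown per dose group, and the groups are small.

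**Working it through.** There is no plan figure to reproduce, so the check is to apply the rules as written.

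**1. One worked case.** Assumed dates: dose 15 March 2019, AE end 10 March 2019. The last column adds the third rule's end-date condition to the first rule, with the earliest possible date as fallback.

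| Start date on record | Rule | Onset as written | Onset with the check |
|---|---|---|---|
| day unknown, March 2019 | first | 15 March | 1 March |
| day and month unknown, 2019 | first | 15 March | 1 January |
| day unknown, February 2019 | second | 1 February | 1 February |
| wholly missing | third | none | none |

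In the first two rows the imputed onset is 15 − 10 = 5 days after the event ended. The second and third rules do not produce this fault.

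**2. Is the fault general within the first rule?** Protocol 4.1 screens within 28 days before transplant, with the dose one day earlier, so take a 27-day pre-dose window (an assumption). Consider every start/end pair in that window, for each dosing date in 2019, equally weighted.

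- Pairs per dosing date: 1 + 2 + … + 27 = 27 × 28 / 2 = 378. All pairs: 365 × 378 = 137,970.
- Day missing: the first rule applies when the start lies in the dosing month. For dosing day d, let m = min(d − 1, 27); the number of pairs is m(m + 1)/2. Days 1 to 28 give 3,654 per month, and 12 × 3,654 = 43,848. Days 29, 30 and 31 occur 11 + 11 + 7 = 29 times, and 29 × 378 = 10,962. Total 54,810, and 54,810 / 137,970 = 39.7%.
- Day and month missing: the start must lie in the dosing year. 3,654 + 337 × 378 = 131,040, and 131,040 / 137,970 = 95.0%.
- In every one of these pairs the imputed onset follows the event's own end, by 1 to 27 days. With the check added, the count is 0 in both settings.

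These percentages describe the rule under an assumed window and uniform weights. They do not estimate how many AEs in this trial are affected.

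**3. Effect on a table cell.** Protocol 7.5.1 gives cohorts of 3, or 6 after expansion. One added patient moves a preferred-term incidence by 1/3 = 33 points or 1/6 = 17 points. VIII.A counts patients with at least one event, so this shift occurs only if the patient has no post-dose event of the same term.

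**4. Medications.** With the same dose date, a known stop on 10 March and a start of unknown day in March, VIII.D imputes the start as 15 March. The stop is not imputed, so the order check does not act, and the record reads start 15 March, stop 10 March.

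**The case against.** The case on the other side has five parts.

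- **Pre-dose events should not be in the AE data**, because the SAP routes them to Medical History. This stands only in part. Protocol 9.2.8.3 puts AEs in the eCRF from consent with a pre-conditioning category, and the third rule's condition has a purpose only if AE records can end before dosing.
- **TEAE status does not depend on imputed onset.** A reader might infer that the first rule turns a pre-dose event into a TEAE. The SAP does not say so. Taken literally, its TEAE sentence covers every AE collected from consent, whatever the onset, and then the end-date check alone would change no table. The next sentence, which treats pre-dose events as baseline, implies a test of onset on or after dosing, but that test is never written. This objection stands. The reversed dates hold under either reading.
- **The case is rare.** The site query must fail, the known date parts must match dosing, and the end must be known well enough to precede dosing. This stands. A reader might put the share affected at about half, since 52% of the days in a 28-day pre-dose period fall in the dosing month (dosing day uniform over days 1 to 30: 434/840). That is a share of days, not of events that ended before dosing.
- **Medications are still classed correctly.** A reader might infer a wrong prior/concomitant class. VIII.D treats any drug stopped before the first dose as prior, whatever its start. This stands, and only the impossible date pair remains.
- **The stakes are low.** The output is descriptive, any error over-counts rather than hides events, and the AE listing shows onset and end, so a reversed pair could be seen. This stands and limits severity.

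**Conclusion.** The gap is real and follows from the SAP text. When the site query fails and a known end precedes dosing, the first rule places onset after the event's end. Wrong counting as treatment-emergent follows only if TEAE means onset on or after dosing, which VIII.A implies without stating. Nothing in the documents gives the number of affected records, and it is probably small. The 33- or 17-point shift is the effect of one such record under that TEAE reading, in a patient with no post-dose event of the same term. For medications the result is a date inconsistency only. Using the dosing date for an event that continues past dosing is not in question. Severity is minor.

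**What to change.** Make three changes to the SAP, which section I.B allows until database lock.

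1. In the first AE rule, use the dosing date only when the event's end date does not fall before it. If it does, use the earliest date consistent with the known parts.
2. State in VIII.A that a TEAE is an AE with onset on or after the tinostamustine dose. Without this the first change corrects the dates but need not change the tables.
3. In VIII.D, add that an imputed start may not be later than a known stop date.

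The cost is three sentences and a small change to the date-derivation code. No new data are needed.

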## **B. Exposure**

Descriptive statistics for the percent of expected tinostamustine dose received and the actual dose received will be summarized. A tabular summary and listing of tinostamustine administration and dose level, and a by-patient listing of the date and time of each study drug dose and the dose administered also will be presented.

Data listings will be provided for the ASC infusion and engraftment data as reported on the eCRFs.

## **C. Clinical Laboratory Results**

For each clinical chemistry (including kidney function tests) laboratory parameter, summary tables displaying the number of non-missing values, mean, standard deviation, median, and range (minimum and maximum) for actual values and changes from baseline for each assessment time point will be prepared. Change from baseline will be calculated as the post-baseline measurement minus the baseline measurement. If either the baseline or post-baseline value is missing, the observation will not be included in the change from baseline summary.

All laboratory test results (including serum chemistry and kidney function tests) will also be presented in data listings for the Safety Population. Any out of range values will be flagged in the data listings.

## **D. Concomitant Medications**

Concomitant medication is defined as any medication with a start date within 28 days prior to the first dose of tinostamustine through Day 100 ( $\pm$  7 days). These medications will be documented as administered pre-conditioning (i.e., pre-tinostamustine); during conditioning (i.e., after the start of the first tinostamustine infusion through immediately before the start of autologous stem cell infusion); or after ASCT (i.e., after the start of ASC infusion). Any medication with a stop date prior to the first dose of study treatment is defined as a prior medication.

If the start date or the end date of a concomitant medication is missing, the following imputation rules will be applied:

Mundipharma-EDO GmbH / Protocol: EDO-S101-1004  
IQVIA Biotech (Confidential) Project # **CCI**

- For either the start or end date, if the year is missing or if the day, month, and year are all missing, do not impute.
- If both the start and stop dates are missing the month or day, the start date will be imputed first. If the imputed stop date is before the start date (imputed or non-imputed), then the stop date will be imputed using the start date.
- For the start date, if the day (or the day and the month) are missing, but all other date components match with the first dose date of study drug, use the first dose date of study drug. Otherwise, if the day (or the day and the month) are missing, but some of the other date components do not match with the first dose date of study drug, use the earliest possible date. For example, use Jan 1 if the day and the month are missing; use the first day of the actual month if only the day is missing.
- For the end date, if only the day is missing, use the last day of the month; if the day and the month are missing, use Dec 31.

Concomitant medications will be coded using the World Health Organization Drug Dictionary (WHO-DD). A separate summary table for each will be organized to display the anatomical main class (1st level) of each coded medication and, within that, the pharmacological subgroup (3rd level) of the coded medication. The summary tables will display counts and percentages of patients who reported using at least one medication in each represented pharmacological subgroup.

A listing of concomitant medications will be generated for the Safety Population and will display entries from the Concomitant Medications eCRF page, ordered within patient by the “Date Started.” The listing will display the recorded term from the CRF and, adjacent to that, the WHO Drug pharmacological subgroup and the anatomical main class that appears in the tables.

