## 7.8. Prior and Concomitant Medications and Procedures

All prescription and non-prescription medications and therapies, including pharmacologic doses of vitamins, herbal medicines, or other non-traditional medicines, taken from 28 days prior to the first dose of tinostamustine through Day 100 ( $\pm 7$  days) must be recorded in the eCRF.

Concomitant medications will be documented as administered pre-conditioning (i.e., pre-tinostamustine); during conditioning (i.e., after the start of the first tinostamustine infusion through immediately before the start of autologous stem cell [ASC] infusion); or after ASCT (i.e., after the start of ASC infusion).

On PK sample collection days (Table 1), both the date and time of concomitant medications and therapies must be recorded.

The Investigator should contact the study medical monitor with any questions or clarifications regarding concomitant medications.

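### Read literally, SAP VIII.D puts a drug started more than 28 days before dosing and still taken at dosing in neither medication table

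*SAP*

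**What the plan says.** **Medications, SAP VIII.D.** The definition of concomitant rests on the start date: "Concomitant medication is defined as any medication with a start date within 28 days prior to the first dose of tinostamustine through Day 100", with a tolerance of a week either way. The definition of prior rests on the stop date: "Any medication with a stop date prior to the first dose of study treatment is defined as a prior medication". The section then repeats the protocol's three administration periods (pre-conditioning, during conditioning, after ASCT) and describes summary tables by drug class. For incomplete dates it says "if the year is missing or if the day, month, and year are all missing, do not impute". Where the recorded parts of a start date differ from the dose date, it takes the earliest possible date: "use the first day of the actual month if only the day is missing". The listing "will display entries from the Concomitant Medications eCRF page".

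**Medications, Protocol version 2.0.** Section 7.8 requires recording of medications "taken from 28 days prior to the first dose of tinostamustine through Day 100" (±7 days). Section 9.1.5 likewise refers to what the patient received. Section 10.2.7 promises tabulations of both prior and concomitant medications. SAP I.C, which lists the analyses dropped when the study was discontinued, does not mention medications.

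**Adverse events.** The first sentence of SAP VIII.A takes adverse events from informed consent through Day 100 (later if drug-related) and labels them treatment-emergent. The second treats every event before the tinostamustine dose as baseline status, to be entered on the Medical History form. Protocol 9.2.8.2, 9.2.8.3 and 9.2.8.4 record adverse events and serious adverse events from consent onward, and 9.2.8.3 gives them a pre-conditioning category.

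**The concern.** The two medication definitions use different dates and do not cover every case between them. The drugs that fall through are the long-term ones that patients were taking when tinostamustine was infused. A concomitant-medication table is normally expected to show these. The protocol collects them, so the loss would occur only at the tabulation step.

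The adverse-event wording raises a lesser form of the same problem. The treatment-emergent label literally begins at consent, before any treatment, and the sentence that takes pre-dose events out again sends them to a place that the protocol does not name. The two treatment-emergent tables are the only adverse-event summary tables that the SAP specifies, so their definition should permit one reading.

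**Working it through.** This is a check of definitions, and the plan gives no figure to reproduce. For counting only, let the tinostamustine dose be day 0. The SAP rules are then:

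- concomitant if the start falls from day −28 through Day 100 (±7 days);
- prior if the stop falls before day 0.

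The protocol rule is: recorded if taken at any time from day −28 through Day 100 (±7 days).

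| Drug use | Start in SAP window? | Stop before dose? | SAP label | Recorded under Protocol 7.8? |
|---|---|---|---|---|
| Start −60, ongoing | no | no | **neither** | yes |
| Start −60, stop +10 | no | no | **neither** | yes |
| Start −29, ongoing | no | no | **neither** | yes |
| Start −28, ongoing | yes | no | concomitant | yes |
| Start −60, stop −5 | no | yes | prior | yes |
| Start −20, stop −5 | yes | yes | both | yes |
| Start +5 | yes | no | concomitant | yes |

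The first three rows are the gap. One day's difference in start date (−29 against −28) decides whether an ongoing drug is tabulated. The double label in the sixth row is compatible with the protocol's pre-conditioning period and is not an error in itself.

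**Incomplete start dates.** There are three cases.

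1. If the start year is unknown, nothing is imputed and the start-date test has no date to work on.
2. If the start is known only to the month of dosing, it is set to the dose date and stays in the window.
3. If the start is known only to the month before dosing, it is set to the 1st of that month. Take an assumed dose date of 15 March 2019 and a start recorded as February 2019. The imputed start is 1 February, which is 27 + 15 = 42 days before dosing and outside the window. The window itself opens on 15 February (13 + 15 = 28 days), so a true start on any of the 14 days from 15 to 28 February was inside it and is moved out.

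More generally, the 1st of the preceding month is at least 30 days before dosing when that month has 30 or 31 days. After a 28-day February it is 28 days before a dose on 1 March and 29 or more before any later March dose. So a start that truly lay in the window but is known only to the preceding month is nearly always moved out. How often such dates occur is not stated.

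**Adverse events.** Take an event with onset on day −10, after consent. By the first sentence of SAP VIII.A it is treatment-emergent. By the second it is medical history. By Protocol 9.2.8.3 it is an adverse event in the pre-conditioning category. An event on or after the dose raises no conflict.

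**The case against.** The strongest reply on medications is that the start-date wording is a slip in paraphrasing the protocol. The SAP keeps the protocol's administration periods, its tables count patients who reported using a drug, and a sensible programmer would include an ongoing long-term drug. That may well be what was meant. It does not remove the point, because the written rule gives a wrong table and a SAP should not depend on the programmer overriding it.

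On adverse events the reply is stronger. The second sentence is specific, directly follows the general one, and reads naturally as an exception that leaves only events from dosing onward. The rule for a completely missing start date agrees with this, since it declines to assign the dose date to an event that ended before dosing. A reader might infer that SAP VIII.A forces two incompatible versions of the treatment-emergent tables. The documents do not support that. If the SAP was followed, pre-dose events sit on the Medical History form and cannot enter the tables under either reading, and nothing shows that any such event exists. What stands is that the label literally starts at consent, no sentence states an onset-or-worsening criterion, and the Medical History instruction departs from the protocol.

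It is also fair to say that the outputs are descriptive, that the trial was discontinued, and that the listings allow any row to be checked.

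**Conclusion.** The medication definition is wrong as written and should be corrected. The adverse-event wording is a secondary clarification. Both are minor in effect. They change only the descriptive medication and treatment-emergent tables. No hypothesis test, interim analysis or decision rule depends on them.

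Two further readings should be resisted. A reader might infer that long-term drugs disappear from the report. They do not, because the medication listing is built from the eCRF page and shows whatever was recorded. A reader might also try to size the problem from small cohorts, where one patient moves a row's percentage a good deal, or from the share of incomplete dates that shift out of the window. The first is true of any one-patient change in any table. The second says nothing without knowing how often such dates occur. The number of affected patients or events cannot be computed from the documents.

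The conclusion rests on a literal reading of SAP VIII.D, and on taking its reference to separate summary tables to mean one for prior and one for concomitant medications.

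**What to change.** **SAP VIII.D.** Define concomitant medication by use: any medication taken at any time from 28 days before the first dose through Day 100 (±7 days), whatever its start date. Include a drug with an unknown start date unless it is known to have stopped before that window. Keep the three administration-period labels. Label as prior those stopped before the first dose, and state that such a drug may also carry the pre-conditioning label. Once the start date no longer decides inclusion, the effect of setting month-only starts to the 1st largely disappears.

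**SAP VIII.A.** Define a treatment-emergent adverse event as one with onset, or worsening, at or after the start of the tinostamustine infusion through Day 100 (±7 days), or later if considered drug-related. Keep pre-dose adverse events and serious adverse events in the All AEs listing, flagged as pre-conditioning. Reconcile the Medical History sentence with Protocol 9.2.8.2 to 9.2.8.4.

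**Cost.** A few sentences, which SAP I.B allows until database lock. The medication change uses dates already collected. If sites entered pre-dose events only as medical history, recovering grade, causality and seriousness might need re-entry at site; the documents do not say whether any such events exist.
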